4.1.11 Estimates for time-to-event analyses

Cox proportional hazards models with stratification factors (including sex, age group [≥ 10 and < 15 years, ≥ 15 and < 18 years] and background antidiabetic medication [metformin only, insulin only, metformin + insulin]) as covariates will be displayed by treatment group. Time to event (in days) will be calculated as: date of event - date of first dose + 1. Subjects that permanently discontinue treatment but remain in the study will be included in the analysis. Subjects who do not have the event will be censored at the Week t visit date or the last visit date for those withdrawing from the study before Week t visit. Subjects lost to follow-up during the applicable period will be censored at their latest assessment date whereas subjects having skipped Week t visit will be censored at their next visit date or the latest Week t assessment date amongst all subjects (whichever is earlier).

Kaplan-Meier plots of time to event variables will be displayed by treatment group. Unless otherwise specified, the plot will be presented only when there are at least 5 "events" in each treatment group. Additionally, a table will accompany the plot and will display the Kaplan-Meier estimates of the cumulative event probabilities (with 95% CI calculated based on Greenwood's method when applicable) of subjects with event at specific time points by treatment group. If the estimated lower bound of 95% CI is below 0 or the estimated upper bound of 95% CI is over 1, then it will be restricted to 0 or 1 respectively. The p-value from a pairwise Log-Rank test (stratified by sex, age, and background medication) of the null hypothesis of no difference between treatment arms in the probability of an event will be presented.

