The proportion of subjects who require glycemic rescue medication or discontinue the study medication due to lack of efficacy at Week 26 will be analyzed using a logistic regression with adjustment for the baseline HbA1c measurement, treatment, and the randomization strata. Ninety five percent confidence intervals for the adjusted percentages/response rate within each treatment group as well as for the adjusted odds ratios for each treatment group and placebo, 95% confidence intervals, and p-value will be calculated with adjustment for baseline HbA1c measurement and randomization strata.

The analysis will use subjects in the primary efficacy data set (i.e., Randomized Subjects Data Set).

Time to glycemic rescue medication or discontinuation of study medication due to lack of efficacy during the 26-week treatment period will be analyzed using a Cox proportional hazards model with stratification factor as covariate. Estimates of the hazard ratio and 95% confidence interval will be provided. Kaplan-Meier estimates will be calculated and plotted by treatment group. For the analysis during the 26-week treatment, all subjects will be censored at the Week 26 visit date or last study date (for those withdrawing from the study prior to Week 26 visit), if rescue or treatment discontinuation due to lack of efficacy has not occurred by then.

These analyses will use subjects from the Randomized Subjects Data Set.

Exploratory efficacy endpoints for short-term and long-term assessment of saxagliptin and dapagliflozin

Change from baseline at Week 52 (LT) in HbA1c and, separately, FPG will be analyzed using an ANCOVA model.

Percentage of subjects with baseline $HbA1c \ge 7\%$ achieving an HbA1c < 7% at Week 52 (LT), will be analyzed using a logistic regression with adjustment for the baseline HbA1c measurement and the randomization strata.

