4.1.10 Proportion of subjects with a pre-defined characteristic (responders) at Week t

The proportion of subjects with a *pre-defined characteristic (responders)* at Week t will be analysed using a weighted or unweighted logistic regression when there are at least 5 responders by treatment group. For proportion of responders (e.g., meeting HbA1c criteria), estimates, confidence intervals, and tests will be obtained using a weighted or unweighted logistic regression. Odds ratios (and corresponding standard errors [SE]) representing the responder odds in the dapagliflozin/saxagliptin treatment group (or regimen) versus placebo group will be generated adjusted for baseline variable (e.g., adjustment for baseline HbA1c) and each randomisation stratification factor using the SAS LOGISTIC procedure.

The frequencies of response/non-response and the associated crude response rates (as percentages) will be presented by treatment group (or regimen). In addition, weighted or non-weighted adjusted percentages, standard errors, and 95% CIs for each treatment group (or regimen) will also be displayed. Adjusted odd ratio and corresponding 95% Log likelihood confidence interval, and p-values (uncorrected) will also be presented.

For the HbA1c responder endpoints, if there is no missing data for all treatment groups in the analysis at Week t, then the logistic regression model or Fisher's exact test will be run on the non-imputed data and no combining of results from each imputed data set is necessary.

In case of non-convergence because of sparse data subsequent backup models will be used in removing randomisation strata in sequential order and/or collapsing the randomisation strata of background medication as defined in Section 4.1. A subsequent back-up model in the order presented Section 4.1 will only be provided if the preceding back-up model does not converge.

When there are less than 5 responders in any treatment group, the unadjusted (and difference) proportions, weighted or non-weighted exact 95% confidence interval, and p-values from the weighted or unweighted Fisher's exact test (when applicable) will be provided.

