4.6 Exploratory efficacy analyses

Exploratory endpoints will not be statistically tested. As with the primary and secondary efficacy analyses, separate models will be used for dapagliflozin and saxagliptin analyses, and each analysis will include the (common) placebo group. Exploratory analyses will be performed for overall dapagliflozin and overall saxagliptin separately, by combining all treatment groups (low-dose and high-dose).

Details are provided below.

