4.6.1 Exploratory efficacy endpoints for short-term period

These analyses will be conducted on the Randomised Subjects Data Set and the comparisons will be between overall dapagliflozin (or saxagliptin) and placebo.

4.6.1.1 Analysis of subjects requiring glycaemic rescue medication or discontinuing study medication due to lack of efficacy

The proportion of subjects requiring glycaemic rescue medication or discontinuing study medication due to lack of efficacy at or prior to Week 26 will be analysed between overall drug treatment (low-dose and high-dose) and placebo using a logistic regression.

This will be analysed using a logistic regression and summarised as described in Section 4.1.10. No weights will be used in the logistic regression for this analysis.

In addition, this analysis will be repeated for the subgroup of subjects on a stable baseline dose of metformin IR or XR (with or without insulin).

4.6.1.2 Time to glycaemic rescue medication or discontinuation of study medication due to lack of efficacy

A time-to-event analysis (where event is first use of rescue medication or discontinuation of study medication due to lack of efficacy, whichever is earlier) during the 26-week treatment period will be analysed using a Cox proportional hazards model as described in Section 4.1.11. Estimates of the hazard ratio and 95% CI will be provided.

In addition, an analysis based on Kaplan-Meier estimates will be calculated and 95% CIs and nominal p-value from a pairwise log rank test will be presented.

Rules for censoring are described in Section 4.1.11.

In addition, both analyses will be repeated for the subgroup of subjects on a stable baseline dose of metformin IR or XR (with or without insulin). No Kaplan-Meier plot will be presented for the subgroup analysis.

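### The exploratory Cox models for time to rescue omit baseline HbA1c, although the logistic model for the same event adjusts for it

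*SAP*

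**What the plan says.** **Time to event.** SAP 4.1.11 uses "Cox proportional hazards models with stratification factors (including sex, age group" and background medication) as covariates. The model is applied to first rescue medication or stopping study drug for lack of efficacy, over 26 weeks (SAP 4.6.1.2) and 52 weeks (SAP 4.6.2.4). Protocol 8.4.2.3 has the same content for the 26-week analysis: "Cox proportional hazards model with stratification factor as covariate". The accompanying test uses the same three factors: "The p-value from a pairwise Log-Rank test (stratified by sex, age, and background medication").

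**Proportion with the event.** For the same composite event, Protocol 8.4.2.3 says it "will be analyzed using a logistic regression with adjustment for the baseline HbA1c measurement, treatment, and the randomization strata". SAP 4.6.1.1 (26 weeks) and 4.6.2.3 (52 weeks) refer to SAP 4.1.10, where the odds ratio is "adjusted for baseline variable (e.g., adjustment for baseline HbA1c) and each randomisation stratification factor".

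**Status.** SAP 4.6 states: "Exploratory endpoints will not be statistically tested". SAP 4.6.1.2 reports the Cox hazard ratio with a 95% CI and says that a "nominal p-value from a pairwise log rank test will be presented".

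**The concern.** One event is analysed twice, and only one analysis uses baseline HbA1c. Children enter with HbA1c between 6.5% and 10.5%. Under Protocol 3.7.2, HbA1c above 8.0% itself requires rescue from Week 26, so in the 52-week analysis a child who starts above 8% avoids rescue only if HbA1c falls. Before Week 26 the trigger is FPG alone. The link is less direct there, but the sponsor chose baseline HbA1c for the 26-week logistic model.

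In a Cox model, omitting a prognostic covariate pulls the estimated hazard ratio towards 1 and costs power, even with perfect randomisation. At stake are the reported hazard ratio, the position of its interval, and how it reads beside an odds ratio that is conditional on baseline HbA1c.

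**Working it through.** **1. The plan's own power figure.** The only stated power is for the primary endpoint (SAP 1.3): difference 0.75, SD 1.7, 81 per arm, two-sided 0.05.

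Power = Φ(0.75 / (1.7 × √(2/81)) − 1.96) = Φ(2.81 − 1.96) = 80.2%. The required n is 2 × (1.96 + 0.842)² × 1.7² / 0.75² = 80.7, so 81 per arm and 243 in total. The figure reproduces, but it says nothing about time to rescue, for which no power or event count is given.

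**2. Inputs for time to rescue.** From the documents: about 81 per arm, so 162 per drug-placebo comparison, and strata of sex (2), age group (2) and background medication (3). Assumed: true hazard ratio 0.5; placebo event proportion 10%, 20% or 50%; hazard ratio per SD of baseline HbA1c of 1.0, 1.5, 2 or 3; exponential times with one administrative censoring point; strata with no effect of their own and independent of HbA1c.

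Approximate events = 81p + 81 × (1 − (1 − p)^0.5):
- p = 0.10: 8.1 + 4.2 ≈ 12
- p = 0.20: 16.2 + 8.6 ≈ 25
- p = 0.50: 40.5 + 23.7 ≈ 64 (64 to 68 in the simulations, depending on prognostic strength)

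**3. Cox power, strata only → strata plus continuous baseline HbA1c** (2,500 simulated trials per cell):

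| HR per SD of HbA1c | about 12 events | about 25 events | about 66 events |
|---|---|---|---|
| 1.0 | 15.3 → 15.6% | 38.7 → 38.5% | 77.8 → 77.4% |
| 1.5 | 15.6 → 16.0% | 34.9 → 36.3% | 74.7 → 77.3% |
| 2 | 14.8 → 16.0% | 33.8 → 37.2% | 69.8 → 79.5% |
| 3 | 13.6 → 16.8% | 30.3 → 38.2% | 58.4 → 79.3% |

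Cross-check with the usual event formula, Φ(ln 2 × √D / 2 − 1.96): D = 66 gives Φ(2.82 − 1.96) = 80%, in line with the adjusted model.

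**4. Where the gain comes from.** In a separate run of 800 trials per cell with about 66 to 68 events, the median estimated hazard ratio was 0.53 without HbA1c and 0.49 with it at 2 per SD, and 0.59 and 0.48 at 3 per SD. The estimate moves away from 1. The standard error of the log hazard ratio does not shrink; in a check under the same assumptions it rose slightly. The benefit is therefore a shift in the estimate and its interval, not a narrower interval on the log scale.

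**5. Type I error.** With a true hazard ratio of 1 and 2,500 trials, the rate was 4.7 to 5.0% with HbA1c and 4.4 to 5.5% without. The smaller run of 800 trials gave 5.0 to 6.9% and 4.6 to 7.2%. Adjustment made no material difference.

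**6. Log-rank test.** The present strata give 2 × 2 × 3 = 12 cells, or 162 / 12 = 13.5 children per cell. Splitting HbA1c at the median gives 24 cells, or 6.75 per cell. Power then changed by −4.1 to +3.9 points and fell in most settings.

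**The case against.** **No planned conclusion depends on this.** The endpoint is exploratory, lies outside the testing hierarchy, and carries only a nominal p-value. This stands. A reader might infer that the trial gives up power for a claim; it does not. A hazard ratio and interval are still reported, and the covariate affects those.

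**The covariate set looks deliberate.** The SAP amendment history (V3.1) records that the Cox and log-rank analyses were aligned on the stratification factors. A reader might also infer a conflict between SAP and protocol, but both list only stratification factors for the Cox model. This explains why the two time-to-event analyses match each other. It does not explain why HbA1c is left out of one analysis of the event and included in the other.

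**HbA1c may not be the best predictor.** No passage calls it the strongest predictor of rescue. With FPG as the only trigger before Week 26, baseline FPG could do as well or better in the 26-week analysis. This stands, and the point needs only that HbA1c be prognostic.

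**The unadjusted hazard ratio is not wrong.** It is a less conditional quantity, and part of the shift on adjustment is non-collapsibility. Sharing a covariate would not make the odds ratio and hazard ratio the same quantity either. This stands, so the present model should not be called biased.

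**The same remedy might seem to suit the log-rank test.** It does not: a continuous covariate cannot be entered as a stratum, and a further split usually cost power.

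**Conclusion.** This is a minor but real inconsistency, with a near-costless improvement confined to the Cox models. Under the assumed inputs the power gain is about 0.4 to 3 points with about 12 events, 1 to 8 with about 25, and 3 to 21 with about 66. With no prognostic effect the change is −0.4 to +0.3 points, so little is risked. Differences of a few tenths of a point are within simulation error.

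The size rests wholly on an event rate, a treatment effect and a prognostic strength that the documents do not supply. The simulations also do not represent the metformin withdrawal and placebo-to-active switches at Week 32 or 40, so they are only a rough guide for the 52-week analysis. No confirmatory result, and no conclusion from the log-rank test, is affected.

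**What to change.** In SAP 4.1.11, add continuous baseline HbA1c (as defined in SAP 4.1.1) to the Cox models used in 4.6.1.2 and 4.6.2.4, or state why it is left out. Label the resulting hazard ratio as conditional on baseline HbA1c. Leave the stratified log-rank test and the Kaplan-Meier estimates as they are. The back-up order in SAP 4.1 removes only strata, so HbA1c would stay in the model if cells are sparse. In 4.6.1.1 and 4.6.2.3, name baseline HbA1c outright, because 4.1.10 mentions it only as an example. The present model can be kept as supportive.

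The cost is one covariate already measured on Day 1. There are two small downsides: the hazard ratio becomes conditional on baseline HbA1c, and the Cox model no longer uses exactly the same factors as the log-rank test. If treatment codes have already been released, the adjusted model should be shown as an additional analysis and marked as not prespecified.

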4.1.12 Multiple imputation

Missing quantitative Week t data at study endpoint will be imputed from one of the 2 missing not at random (MNAR) imputation models for missing Week t data.

The preferred model will be to use a "retrieved drop-out" multiple imputation (MI-RD) model to represent the MNAR process. This will be used if there is sufficient data from 'retrieved drop-outs', defined as subjects who discontinued the treatment (but not the study) and had a Week t HbA1c value. If any of the required imputation models needed for any of the regimens (low, low/high, overall) within dapagliflozin or saxagliptin have less than 5 retrieved drop-out

observations available to fit the model, then MI-WO “wash-out” method will be used for analyses of all regimens for that endpoint. This is a “copy to reference method”. Both MI-RD or MI-WO will be implemented using a baseline to predict Week t values in the MNAR model. The randomisation strata will be coded using indicator variables as follows and used in the multiple imputation steps:

- randomisation strata of background medication will be coded as
 - met (1) and ins (0) if metformin only,
 - met (0) and ins (1) if insulin only,
 - met (0) and ins (0) if metformin + insulin;
- randomisation strata of background medication if randomisation strata of insulin only and insulin with metformin are grouped will be coded as
 - metins (1) if metformin only,
 - metins (0) if insulin only or insulin with metformin;
- randomisation strata of age group will be coded as
 - age (1) if age ≥ 10 and < 15 years,
 - age (0) if age ≥ 15 and < 18 years;
- randomisation strata of sex will be coded as
 - sex (1) if male,
 - sex (0) if female.

Each imputation model will use a common seed value of 2717.

In case of non-convergence because of sparse data, subsequent backup imputation models will be used in removing randomisation strata in sequential order and/or collapsing the randomisation strata of background medication as defined in Section 4.1. A subsequent back-up model in the order presented Section 4.1 will only be provided if the preceding back-up model does not converge.

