4. ANALYSIS METHODS

4.1 General principles

SAS version 9.4, or higher, will be used to produce all tables, listings, and figures. All table, listing, and figure specifications are provided as separate documents; these must be read in conjunction with the corresponding SAP version.

The confirmatory analyses of the primary and secondary endpoints within each drug (dapagliflozin vs. placebo and saxagliptin vs. placebo) will be performed using a hierarchical testing approach within each drug at the two-sided 0.05 level (with corresponding 95% CIs). No comparisons will be performed between dapagliflozin and saxagliptin.

When fitting models which involve the stratification variables, in case of non-convergence the stratification level may be combined with other levels or one or more stratification variables may be removed from the model.

For each imputation and statistical model described below adjusted on randomisation strata, in case of non-convergence (i.e.: because of sparse data), the following back-up models will be used in the presented order:

- 1) Remove randomisation strata of sex,
- 2) Remove randomisation strata of sex and age,
- 3) Remove randomisation strata of sex and age and collapse randomisation strata of background medication in two modalities to present (metformin only and insulin only grouped with metformin + insulin),
- 4) Remove randomisation strata of sex, age and background medication.

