4.1.12.2 Retrieved Drop-Outs Multiple Imputation Method

Missing HbA1c/FPG data will be imputed separately by treatment regimen of each drug (i.e., low-dose, low-dose/high-dose, and placebo) and weight (as applicable). Subjects not going through up-titration randomisation due to discontinuation of study medication will be assigned a weight of 1 and imputed in the both the low-dose and low-dose/high-dose regimens.

Using monotone datasets generated as described in Section 4.1.12.1, the remaining missing HbA1c/FPG data will be imputed separately for each treatment group and weight (as applicable) using a REGRESSION method in conjunction with the MONOTONE statement and the MNAR statement of the SAS MI procedure.

- Step 1: The imputation model used to create monotone data pattern (see Section 4.1.12.1) will include factors and covariates in the following order: indicators representing randomisation strata of sex, age group and background medication, baseline HbA1c/FPG as well as HbA1c/FPG from all visits per protocol up to Week t.
- Step 2: Using an imputation model with terms for indicators representing randomisation strata of sex, age group and background medication, baseline HbA1c/FPG followed by Week t HbA1c/FPG, for each treatment regimen and weight, subjects that discontinue treatment prior to Week t with baseline and an (off-treatment) Week t assessment available will be used to impute within each missing Week t values (for that treatment regimen) after baseline. Separate models will be performed for each treatment regimen and weight (as applicable) to impute Week t missing data in the multiply imputed monotone datasets generated by Step 1. For this step, one imputation will be performed for each of the 200 imputed datasets from Step 1 to form “complete datasets”.
- Step 3: Imputed values from each of the 200 imputation datasets selected from Step 2 and the non-missing data will be used to calculate change from baseline. The HbA1c/FPG change from baseline values at Week t will be analysed by an ANCOVA with terms for baseline HbA1c/FPG, randomisation strata, and treatment group as described in Section 4.1.9. In case of non-convergence, the imputation and ANCOVA model will be simplified by removing/collapsing the randomisation strata indicator variables in a stepwise manner as described in Section 4.1.

- Step 4: Results from each ANCOVA model will be combined as described in Section 4.1.12.4.

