If convergence in all treatment regimens (including placebo) is still not achieved the alternative imputation method (MI-washout) will be used.

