4.4 Primary efficacy endpoint analysis

4.4.1 Primary analysis of the primary endpoint

The primary efficacy analysis will compare the mean reduction in HbA1c from baseline at Week 26 between overall drug treatment (low-dose and high-dose) and placebo. The ITT estimand (which will be estimated using data regardless of premature treatment discontinuation, regardless of rescue medication initiation and with multiple imputation) will be evaluated as the primary estimand.

Listings of HbA1c and FPG results used for the efficacy analysis will be presented with flags to identify data collected prior to rescue medication initiation or treatment discontinuation.

The primary efficacy analysis will be performed using an ANCOVA model, as described in Section 4.1.9. Separate models will be used for dapagliflozin and saxagliptin analyses, and each analysis will include the (common) placebo control. Each model will have terms for baseline HbA1c value, treatment group, and randomisation strata variables (age group, sex and background medication). Missing values for Week 26 will be imputed using multiple imputation method assuming the data are not missing at random. No weights will be used in the multiple imputation or ANCOVA for this analysis.

An overview of the analysis steps are as follows:

- i) Impute missing Week 26 HbA1c data using multiple imputation (as described in Section 4.1.12).
- ii) Analyse data by applying the ANCOVA model (described in Section 4.1.9) in each of the imputed data sets to calculate the LS means and corresponding SEs for the adjusted mean changes within each treatment group as well as for the differences in adjusted mean changes

between treatment groups. If any stratification variables in the imputation model are collapsed, then the ANCOVA model will be collapsed correspondingly.

- iii) Combine point estimates and SEs using Rubin's rules (as per Section 4.1.12.4) to produce valid global estimates with corresponding p-values and CIs.

Combined LS means and 95% confidence intervals for the mean change in HbA1c for each treatment group as well as the difference in the estimated mean change between the dapagliflozin/saxagliptin treatment group and placebo will be calculated. The p-value of the difference in Week 26 estimates between dapagliflozin/saxagliptin and placebo will be presented.

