Both the MI-RD and wash-out imputation methods will be presented for the primary endpoint. If all of the imputation models have at least 5 observations, then MI-RD will be the primary analysis and wash-out will be the sensitivity analysis. Conversely, if any of the imputation models have less than 5 observations, then wash-out will be the primary analysis and MI-RD will be the sensitivity analysis. A summary of the number and percentage of subjects who were retrieved drop-outs will be presented by visit for the ST period for both HbA1c and FPG.

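### The retrieved drop-out imputation can become primary on 5 observations although its model has 6 coefficients, and only an undefined non-convergence rule steps it down

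*SAP*

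**What the plan says.** **Entry rule.** SAP 4.1.12 prefers MI-RD. It switches all regimens of an endpoint to wash-out imputation (MI-WO) if any of the required models "needed for any of the regimens (low, low/high, overall) within dapagliflozin or saxagliptin have less than 5 retrieved drop-out" observations. SAP 4.4.1 words the rule more broadly: "If all of the imputation models have at least 5 observations, then MI-RD will be the primary analysis"; otherwise wash-out is primary. Both methods are presented either way.

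**Model.** Step 2 in 4.1.12.2 is fitted to retrieved drop-outs only, with "terms for indicators representing randomisation strata of sex, age group and background medication, baseline HbA1c/FPG followed by Week t HbA1c/FPG". Section 4.1.12 codes background medication as two indicators. Step 2 also says: "Separate models will be performed for each treatment regimen and weight (as applicable) to impute Week t missing data". For the primary endpoint, 4.4.1 states: "No weights will be used in the multiple imputation or ANCOVA for this analysis".

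**Step-down.** SAP 4.1 says that "in case of non-convergence (i.e.: because of sparse data), the following back-up models will be used in the presented order": drop sex; drop sex and age; also collapse background medication to two levels; drop all strata. Section 4.1.12 adds: "A subsequent back-up model in the order presented Section 4.1 will only be provided if the preceding back-up model does not converge". At the end of 4.1.12.2: "If convergence in all treatment regimens (including placebo) is still not achieved the alternative imputation method (MI-washout) will be used".

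**Weights.** Under 4.1.12.1 and 4.1.12.2, subjects who stop study drug before up-titration get weight 1 and enter both regimens' imputation models.

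**The concern.** The entry threshold is below the number of parameters in the model that it admits. Whether a smaller model then replaces it depends on one undefined word. A normal linear regression has a direct solution and does not iterate, so a full-rank fit on 1 residual df does not fail to converge in any ordinary sense.

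The danger is in the imputation draw. Each imputation draws the residual variance as RSS divided by a chi-square variable on the residual df. On 1 or 2 df that draw is extremely variable. The between-imputation variance, and hence the Rubin standard error, can then be large even when only a few values are missing.

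What is at stake is the formal test. The count decides whether MI-RD or wash-out gives the primary p-value, and that p-value opens the hierarchy in SAP 4.5.1.

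**Working it through.** **1. The plan's own figure.** Inputs from SAP 1.3: 81 per arm (243 in three arms), difference 0.75, SD 1.7, two-sided alpha 0.05. SE = 1.7 × √(2/81) = 0.267; 0.75/0.267 = 2.81; power = Φ(2.81 − 1.96) = 80%. This reproduces the stated figure, which assumes that all 243 are analysed.

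**2. Coefficients and residual df.** Intercept 1 + sex 1 + age 1 + background 2 + baseline 1 = 6. The four back-ups have 5, 4, 3 and 2. Residual df = n − coefficients:

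| n | full (6) | back-up 1 (5) | back-up 2 (4) | back-up 3 (3) | back-up 4 (2) |
|---|---|---|---|---|---|
| 5 | −1 | 0 | 1 | 2 | 3 |
| 6 | 0 | 1 | 2 | 3 | 4 |
| 7 | 1 | 2 | 3 | 4 | 5 |
| 8 | 2 | 3 | 4 | 5 | 6 |

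If the ladder stops at the first full-rank model with any residual df, it stops on 1 df at n = 5, 6 and 7 and on 2 df at n = 8. The mean of 1/chi-square(df) is 1/(df − 2), which is finite only above 2 df. That is why 3 is a natural minimum.

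**3. Power of the primary test (simulation).** From the documents: the planning values in step 1, 200 imputations, Rubin's rules, the ladder in 4.1, and ANCOVA collapsed to the same step (4.4.1). Assumed: 2 missing per arm, 15 retrieved drop-outs on active, the full effect kept in drop-outs, and two background-medication mixes (50/10/40% and equal thirds). There were 1,500 trials per cell, with a Monte Carlo error of about 2.5 points. Ranges cover both mixes and the ladder applied per arm or in common.

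| Placebo retrieved drop-outs | first model with ≥1 df | ≥3 df required |
|---|---|---|
| 5 | 35-51% | 74-76% |
| 6-7 | 30-56% | 73-76% |
| 8 | 60-69% | 72-75% |
| 10 | 73-75% | 74-76% |

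With 5 missing per arm, placebo at 5 to 7 gives 23-48% against 61-66%. A second implementation drops empty strata columns and keeps all strata in the ANCOVA. With 2 missing it gives 16, 20, 35 and 60% at placebo 5, 6, 7 and 8. Direction and mechanism agree; the size depends on implementation.

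Type I error at zero difference was 0.4-2.1% (1 df) and 1.9-4.4% (3 df), so there is no inflation.

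**4. How often a model could sit at 5-8.** The documents give no retrieved drop-out counts. Assumed: one retrieved drop-out rate for all subjects; active cells (responders / re-randomised low / re-randomised high) of 41/20/20, 27/27/27 or 21/30/30; discontinuation uniform over 26 weeks. A fraction 14/26 of the re-randomised cells' drop-outs then falls before Week 14 and moves to weight 1.

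- *(a) Counted per model and weight.* The weight-1 model, both weight-2 models and placebo each need 5. The unweighted active model of the primary then has at least 5 + 5 + 5 = 15. Placebo at 5-8 with MI-RD chosen has probability of at most about 0.03%. MI-RD is chosen at all in about 0.1-2% of trials at a 20% rate and 0.6-6.5% at 25%. When it is chosen, a weight-2 model behind secondary tests 1 and 2 is nearly always at 5-8.
- *(b) Counted per regimen.* Weight-1 subjects count in both regimens, so the whole active arm can qualify with as few as 5. MI-RD chosen with an arm of the primary at 5-8 has probability of about 49-54% at an 11% rate. It is 25-42% if all drop-outs are left in their own cells, and about 2% at a 20% rate.

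**The case against.** **The per-model reading is better supported.** SAP 4.1.12 speaks of required models, 4.1.12.2 fits by regimen and weight, and 4.4.1 refers to all the models. On that reading the primary is almost never exposed. This stands, and it is the main limit on the point. It does not settle the matter, because 4.1.12 also lists low, low/high and overall as the units and never says that the count is by weight.

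**The ladder may be driven by sparsity.** SAP 4.1 links non-convergence to sparse data, and Protocol 8.4.2 uses sparseness within strata as its trigger. If a sparse fit runs down to baseline only, little is lost. That is a fair reading, but the SAP gives no sparsity criterion.

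**Other analyses are shown.** Wash-out, missing-at-random and tipping-point results accompany the primary (SAP 4.4.1, 4.4.2), so instability would be visible. They remain sensitivity analyses, and changing the formal test after seeing a large SE would be post hoc.

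**Stronger readings that the documents do not support.** A reader might infer that secondary tests 1 and 2 are often exposed: with equal retrieved drop-out rates in every cell, MI-RD would be chosen in 13-28% of trials at a 20% rate and 34-60% at 25%. Sections 4.1.12.1 and 4.1.12.2 contradict that assumption. Early discontinuations get weight 1, so a weight-2 model holds only those who stop after up-titration. A reader might also infer that the primary test is likely to fail. Nothing in the documents gives the counts needed to say so.

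**Conclusion.** The defect is real and conditional. At 5 or 6 observations the specified model has no residual df, and what follows depends on how non-convergence is read. At 7 or 8 it can be full rank on 1 or 2 df, and nothing steps it down.

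The consequence is lost power in the formal MI-RD test. The loss is large when a model sits at 5-7, smaller at 8 and negligible by 10. It is nil if no Week 26 value is missing. It requires both the first-full-rank reading of the ladder and a low count in a model that is used. The low count is improbable for the primary under per-model-and-weight counting and plausible under per-regimen counting at retrieved drop-out rates near 11%.

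All counts, rates and power percentages are illustrative. They rest on assumed missingness and timing, and none was run in the SAS MI procedure.

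**What to change.** 1. In SAP 4.1.12, either prespecify a baseline-only Step 2 model (already back-up 4 in 4.1), or set a minimum residual df, for example 3, for every MI-RD model including placebo. Make that minimum, in place of non-convergence, the trigger for stepping down the ladder and then for making wash-out primary. At 5 observations the baseline-only model leaves exactly 5 − 2 = 3 df, so this minimum can be met at the existing threshold.
2. Name the placebo model in the 4.1.12 threshold so that it agrees with 4.4.1. State whether the 5 is counted per regimen or per regimen and weight.

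Section 4.4.1 collapses the ANCOVA along with the imputation model. If a baseline-only Step 2 is prespecified, also state whether the ANCOVA keeps its strata.

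The cost is SAP wording only. Step 2 adjusts for fewer covariates, or wash-out is primary more often.
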